2.6.2 Analysis supporting secondary objectives

2.6.2.1 Secondary endpoint(s)

The secondary endpoints of the scenario with ISS7 and HSS7 as the co-primary efficacy endpoints as follows:

1. Improvement of UAS7 at Week 12, assessed as absolute change from baseline in UAS7 score at Week 12
2. Disease activity control at Week 12, assessed as % of participants achieving $UAS7 \leq 6$.
3. Complete absence of hives and itch at Week 12, assessed as % of participants achieving $UAS7 = 0$.
4. Disease activity control at Week 2, assessed as proportion of participants achieving $UAS7 \leq 6$.
5. No impact on participants' dermatology quality of life at Week 12, assessed as proportion of participants achieving $DLQI = 0-1$.
6. Cumulative number of weeks that participants achieve $UAS7 \leq 6$ responses between baseline and Week 12.
7. Cumulative number of weeks that participants achieve $AAS7 = 0$ responses between baseline and Week 12.

For derivation of each endpoint, please see [Section 2.5.2.1](#).

Secondary estimand

See [Section 2.5.1.1](#) for UAS7 score change from baseline at Week 12, and [Section 2.5.2.1](#) for others.

2.6.2.2 Statistical hypothesis, model, and method of analysis

Statistical model, hypothesis, and method of analysis for scenario with ISS7/HSS7 as the co-primary efficacy endpoints

Testing strategy

The following null hypotheses (H_0) will be tested against the respective alternative hypotheses (H_A) in a closed testing procedure ([Bretz et al 2009](#)), thus controlling the family-wise type I error which is set to 0.025 (one-sided):

Co-Primary:

- **ISS7 score change from baseline at Week 12**
- **HSS7 score change from baseline at Week 12**

$H_{01a}: \mu_{\text{remibrutinib}} \geq \mu_{\text{Placebo}}$ versus $H_{A1a}: \mu_{\text{remibrutinib}} < \mu_{\text{Placebo}}$

where μ is the mean change from baseline in ISS7 at Week 12.

$H_{01b}: \mu_{\text{remibrutinib}} \geq \mu_{\text{Placebo}}$ versus $H_{A1b}: \mu_{\text{remibrutinib}} < \mu_{\text{Placebo}}$

where μ is the mean change from baseline in HSS7 at Week 12.

The union null hypothesis is rejected if both elementary null hypotheses (H_{01a}, H_{01b}) are rejected.

Secondaries:

- **UAS7 score change from baseline at Week 12**

$H_{02}: \mu_{\text{remibrutinib}} \geq \mu_{\text{Placebo}}$ versus $H_{A2}: \mu_{\text{remibrutinib}} < \mu_{\text{Placebo}}$

where μ is the mean change from baseline in UAS7 at Week 12,

- **UAS7 ≤ 6 at Week 12**

$H_{03}: p_{\text{remibrutinib}} \leq p_{\text{Placebo}}$ versus $H_{A3}: p_{\text{remibrutinib}} > p_{\text{Placebo}}$

where p is the proportion of participants achieving UAS7 ≤ 6 at Week 12,

- **UAS7 = 0 at Week 12**

$H_{04}: p_{\text{remibrutinib}} \leq p_{\text{Placebo}}$ versus $H_{A4}: p_{\text{remibrutinib}} > p_{\text{Placebo}}$

where p is the proportion of participants achieving UAS7 = 0 at Week 12,

- **UAS7 ≤ 6 at Week 2**

$H_{05}: p_{\text{remibrutinib}} \leq p_{\text{Placebo}}$ versus $H_{A5}: p_{\text{remibrutinib}} > p_{\text{Placebo}}$

where p is the proportion of participants achieving UAS7 ≤ 6 at Week 2,

- **DLQI = 0/1 at Week 12**

$H_{06}: p_{\text{remibrutinib}} \leq p_{\text{Placebo}}$ versus $H_{A6}: p_{\text{remibrutinib}} > p_{\text{Placebo}}$

where p is the proportion of participants achieving DLQI = 0/1 at Week 12,

- **Cumulative number of weeks with an UAS7 ≤ 6 response between baseline and Week 12**

$H_{07}: \mu_{\text{remibrutinib}} \leq \mu_{\text{Placebo}}$ versus $H_{A7}: \mu_{\text{remibrutinib}} > \mu_{\text{Placebo}}$

where μ is the mean cumulative number of weeks that participants achieve UAS7 ≤ 6 response between baseline and Week 12,

[figure not shown]
- **Cumulative number of weeks with an AAS7 = 0 response between baseline and Week 12**

$H_{08}: \mu_{\text{remibrutinib}} \leq \mu_{\text{Placebo}}$ versus $H_{A8}: \mu_{\text{remibrutinib}} > \mu_{\text{Placebo}}$

where μ is the mean cumulative number of weeks that participants achieve AAS7 = 0 response between baseline and Week 12,

A graphical representation of the testing strategy is presented in [Figure 2-2](#).

Figure 2-2 Testing strategy with ISS7/HSS7 as the co-primary endpoints

The value inside the circle represents the significance level. The arrow and value inside the square represent the "alpha-propagation".

The first two hypotheses are tested: both H_{1a} and H_{1b} are tested with full level alpha (0.025 one-sided) and only if both are rejected, then H_2 hypothesis is tested with full-level alpha; otherwise, the testing procedure stops. The testing is strictly hierarchical, so that null hypotheses can be tested along the pre-defined order at the level assigned until a null hypothesis cannot be rejected, at which point the testing stops. Furthermore, the testing strategy reflects the separation of primary and secondary endpoints, so that hypotheses related to secondary endpoints will only be tested if both null hypotheses related to the co-primary endpoints are rejected.

Statistical model and method of analysis

See [Section 2.5.1.2](#) for UAS7 score change from baseline at Week 12, and [Section 2.5.2.2](#) for others.

2.6.2.3 Handling of intercurrent events

See [Section 2.5.1.3](#) for UAS7 score change from baseline at Week 12, and [Section 2.5.2.1](#) for others.

2.6.2.4 Handling of missing values

See [Section 2.5.2.4](#)

2.6.2.5 Sensitivity analyses

Not applicable.

2.6.2.6 Supplementary analyses

See [Section 2.5.2.6](#)

2.7 Safety analyses

For all safety analyses, the safety set will be used. All listings and tables will be presented by treatment group and by visit.

Safety summaries (tables, figures) include only data from the on-treatment period with the exception of baseline data which will also be summarized where appropriate (e.g., change from baseline summaries).

For details of the on-treatment period, please see [Section 2.1.1.4](#).

2.7.1 Adverse events (AEs)

All information obtained on adverse events will be listed by treatment group and participant.

The number (and percentage) of participants with treatment emergent adverse events (the events which occurred during the on-treatment period, TEAE) will be summarized by study period in the following ways:

- by treatment group, primary system organ class and preferred term.
- by treatment group, primary system organ class, preferred term and maximum severity.
- by treatment group, Standardized MedDRA Query (SMQ, narrow) and preferred term.

Separate summaries will be provided for study medication related adverse events, death, serious adverse events, other significant adverse events leading to discontinuation by study period and treatment group.

The most common adverse events reported ($\geq 3\%$ in any group for each preferred term in the SOC-PT table or $\geq 3\%$ in any group for each SMQ table) will be presented in descending frequency according to its incidence in LOU064A 25mg bid starting from the most common event. The cut-off of 3% can be re-evaluated based on number of participants and events.

In these summary tables, a participant with multiple adverse events within a primary system organ class is only counted once towards the total of the primary system organ class.

In the summary of AEs by severity, if a participant reported more than one adverse event with the same preferred term, the adverse event with the greatest severity will be presented. If a participant reported more than one adverse event within the same primary system organ class, the participant will be counted only once with the greatest severity at the system organ class level.

In addition, for adverse events and serious adverse events, exposure adjusted incidence rates will be estimated by treatment group for the double-blind period and for the entire study period. The rate estimates will be reported with exact Poisson 95% CIs (Garwood 1936, Sahai and Khurshid 1993). Please see [Section 5.4.2.4](#) for details.

For infections and infestations (SOC), the number (and percentage) of participants with this event will be summarized by treatment group, SOC, HLGT, HLT and PT for the double-blind period and the entire study period.

[Table 2-13](#) presents overview of analyses on TEAEs.

Table 2-13 Overview of safety analyses on TEAEs

Analysis	Study period	Treatment groups	AEs, SAEs, AESI	AEs by severity, AEs by SMQ, Study med. related AEs, Death, AEs leading to discontinuation
Primary analysis	Double blind	
• LOU064 25mg• Placebo	Crude incidence EAIR	Crude incidence
	Entire study	
• LOU064 25mg• Placebo• Transitioned to LOU064 25mg (under LOU064 treatment)	Crude incidence EAIR	Crude incidence
Final analysis	Entire study	
• LOU064 25mg• Placebo• Transitioned to LOU064 25mg (under LOU064 treatment)	Crude incidence EAIR	Crude incidence

EAIR: Exposure Adjusted Incidence Rate, AESI: Adverse Events of Special Interest

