Final efficacy and safety analyses will be conducted on the entire study period (all periods of double blind, open label and safety follow up).

[figure not shown]
The treatment groups and the data to be used for final analysis are shown in [Table 2-2](#).

Please note: efficacy analysis for “Placebo – LOU064 25mg “treatment group will be provided for all participants initially randomized to placebo regardless of entering the open-label treatment. The efficacy data from baseline to Week 24 will be assessed under placebo. The data after the first dose of LOU064 will be assessed under LOU064 25mg treatment, but separated from the LOU064 25mg treatment group (participants initially randomized to LOU064). Safety analysis for “Transitioned to LOU064” group will be conducted using safety data after switching to LOU064 25 mg treatment.

Table 2-2 Treatment groups for final analyses

Endpoint	Period	Treatment group	Details
Efficacy	Entire study (DB period + OL period)	LOU064 25mg	Participants initially randomized to LOU064 Efficacy from baseline to Week 52
		Placebo - LOU064 25mg	Participants initially randomized to placebo regardless of entering into OL period, i.e. including participants who discontinued during DB period and not entered into OL period, participants who entered into OL period and switched to LOU064. Efficacy from baseline up to Week 52. Note: the data from baseline to Week 24 is under placebo, the data after the first dose of LOU064 is under LOU064 25mg
Safety	Entire study (DB period + OL period + FW period)	LOU064 25mg	Participants initially randomized to LOU064 Safety from baseline up to the end of study
		Placebo	Participants initially randomized to placebo Safety from baseline up to Week 24
	Transitioned to LOU064 25mg	Participants initially randomized to placebo and switched to LOU064 25mg Safety after switching to LOU064 up to the end of study	

DB: double-blind, OL: open-label, FW: follow-up

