2.1.1.4 On-treatment period for safety assessment

The On-treatment period is defined as the period from the first date of dose intake of treatment to the last date of dose intake + a period of time accounting for remaining exposure to drug in relation to the potential pharmacodynamic effects of remibrutinib. It is the reference period for safety analyses on adverse events, laboratory, vital signs, etc.

Remibrutinib has a short half-life (5hrs). Due to the covalent-binding mode, pharmacodynamic effects, including target inhibition in tissues and cells is to be taken into account for determining the follow-up time after the last study drug dose, which is beyond 5 half-lives'. As a conservative measure, 28 days was selected.

Double blind period

The on-treatment DB period will be defined as

- starting from the date of the first actual dose intake of DB treatment and
- ending at the minimum between (i) the date of the last actual dose intake of DB treatment plus 4 weeks (28 days) or (ii) the end of DB period

The end of DB period is minimum of (one day before the date of the first actual dose intake of OL treatment, or the date of study discontinuation, or safety follow-up).

For the participants who entered open-label period more than 28 days later than the last actual dose intake of DB treatment, their end date of on-treatment DB period is defined as one day before the date of the first actual dose intake of OL treatment.

The safety assessment performed at the visit on the day of the first actual dose intake of OL treatment belongs to DB period, assuming that this assessment is performed before the actual dose intake of OL treatment.

This definition will be applied to both of LOU064 25mg treatment group and placebo group.

Entire study period

At the primary analysis, for LOU064 25mg group, the on-treatment period for entire study period will be defined as

- starting from the date of the first actual dose intake of LOU064 treatment i.e., the first day of LOU064 DB treatment
- ending at the minimum between (i) the date of the last actual dose intake of LOU064 treatment plus 4 weeks (28 days) or (ii) the end of study

The end of study is either the date of Week 52 visit, or study discontinuation, or study completion, or safety follow-up visit or cut-off date of primary analysis, depending on participant's status.

For Transitioned to LOU064 25mg group, the on-treatment period for entire study period will be defined as

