- starting from the date of the first actual dose intake of LOU064 treatment (i.e., the first day of LOU064 OL treatment)

- ending at the minimum between (i) the date of the last actual dose intake of LOU064 OL treatment plus 4 weeks (28 days) or (ii) the end of study

The end of study is either the date of Week 52 visit, or study discontinuation, or study completion, or safety follow-up visit or cut-off date of primary analysis, depending on participant's status.

For Placebo group, the definition of on-treatment period is same as the on-treatment DB period.

At the final analysis, for LOU064 25mg group, the on-treatment period for entire study period will be defined as

- starting from the date of the first actual dose intake of LOU064 treatment (i.e., the first day of LOU064 DB treatment) and
- ending at the minimum between (i) the date of the last actual dose intake of LOU064 treatment plus 4 weeks (28 days), or (ii) the end of study

The end of study is either the date of Week 52 visit, or study discontinuation, or study completion, or safety follow-up visit.

For Transitioned to LOU064 25mg group, the on-treatment period for entire study period will be defined as

- starting from the date of the first actual dose intake of LOU064 treatment (i.e., the first day of LOU064 OL treatment) and
- ending at the minimum between (i) the date of the last actual dose intake of LOU064 treatment plus 4 weeks (28 days), or (ii) the end of study

The end of study is either the date of Week 52 visit, or study discontinuation, or study completion, or safety follow-up visit.

For Placebo group, the definition of on-treatment period is same as the on-treatment DB period.

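### Entire-study safety tables set crude percentages over up to 52 weeks on remibrutinib beside 24 weeks on placebo, and the final analysis lists no matched 24-week table

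*SAP*

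**What the plan says.** SAP 2.1.1.1 states: "Final efficacy and safety analyses will be conducted on the entire study period". In Table 2-2 the final safety window for LOU064 25 mg is "Safety from baseline up to the end of study" and for placebo it is "Safety from baseline up to Week 24". A third column holds former placebo participants after they switch.

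SAP 2.1.1.4 applies the same split to the on-treatment period: "For Placebo group, the definition of on-treatment period is same as the on-treatment DB period". For a participant who continues, that period closes the day before the first open-label dose. The LOU064 period runs through open label to 28 days after the last dose or the end of study, whichever is earlier. At the primary analysis it also stops at the data cut-off.

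SAP 2.7.1 provides that "for adverse events and serious adverse events, exposure adjusted incidence rates will be estimated by treatment group", and Table 2-13 adds adverse events of special interest (AESI). The last column of that table, "AEs by severity, AEs by SMQ, Study med. related AEs, Death, AEs leading to discontinuation", has crude incidence only. Laboratory notables (2.7.3, Table 2-14) are numbers and percentages of participants.

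For the primary analysis, Tables 2-13 and 2-14 each have a double-blind row (LOU064 against placebo) and an entire-study row. For the final analysis they have the entire-study row alone, although the text of 2.7.1 asks for AE summaries by study period.

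**The concern.** A crude percentage counts everyone who has had the event by the end of the window, so it grows with the length of the window. Two columns with windows of 24 and 52 weeks will differ even if the drug does nothing. The outputs left crude (severe events, related events, events leading to discontinuation) are among those a reader turns to first for tolerability, which is a secondary objective. Protocol 4.1 also justifies placebo to Week 24 partly because it supplies a background rate for safety findings. The SAP accepts the need for exposure adjustment for AEs, SAEs and AESI in the same table row, and gives no reason for leaving the last column out.

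**Working it through.** The plan states no figure to reproduce here, and no expected 24-week incidence for these outputs. Placebo incidence by Week 24 (p) is therefore an assumption, taken from 3% to 30%.

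**Inputs.** Double-blind period 24 weeks; planned treatment 52 weeks (56 with the full 28-day tail); allocation 300:150; about 10% drop-out by Week 12 (SAP 3.1). Scheduled post-baseline laboratory visits are Weeks 2, 4, 8, 12, 16, 20 and 24 (7), then 32, 40 and 52 (10 in all), or 11 with Week 56.

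**Exposure ratio.** 52/24 = 2.17; with the tail, 56/24 = 2.33.

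**Equal constant hazard.** h = −ln(1 − p)/24, and crude incidence over 52 weeks = 1 − exp(−52h). For p = 5%: h = 0.05129/24 = 0.002137 per week, 52h = 0.1111, incidence 10.5%, ratio 2.10.

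**Other assumptions.**
- Drop-out at weekly rate d: incidence by T weeks = h/(h+d) × [1 − exp(−(h+d)T)] in each arm.
- Front-loaded events, Weibull shape k: ratio = [1 − (1 − p)^((52/24)^k)]/p.
- Detection only at scheduled visits: ratio = [1 − (1 − p)^(n/7)]/p, with n = 10 or 11.

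Ratio of crude percentages, LOU064 to placebo, with identical risk in both arms:

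| Assumption | p = 3% | 5% | 10% | 30% |
|---|---|---|---|---|
| Constant hazard, 52 weeks | 2.13 | 2.10 | 2.04 | 1.79 |
| Constant hazard, 56 weeks | 2.29 | 2.26 | 2.18 | 1.88 |
| Drop-out 20% by Week 52 | 2.01 | 1.99 | 1.93 | 1.71 |
| Drop-out 10% by Week 12, continuing | 1.90 | 1.88 | 1.83 | 1.63 |
| Front-loaded, k = 0.7 | 1.70 | 1.69 | 1.66 | 1.53 |
| Front-loaded, k = 0.5 | 1.46 | 1.45 | 1.44 | 1.36 |

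For laboratory notables, 10 against 7 visits gives 1.42, 1.41 and 1.40 at 3%, 5% and 10%; 11 against 7 gives 1.56, 1.55 and 1.53.

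In percentages under a constant hazard over 52 weeks: 3% becomes 6.4%, 5% becomes 10.5%, 10% becomes 20.4% and 30% becomes 53.8%. At 50% the ratio is down to 1.55.

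**Scale of the artefact.** With 300 and 150 participants and no true difference, a naive two-sided 5% comparison of the 52-week and 24-week percentages would look significant about 31%, 50% and 82% of the time at p = 3%, 5% and 10%. No such test is planned; this only shows how persuasive the gap could look.

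**What each remedy does.** Cutting both arms at Week 24 gives a ratio of 1.00 by construction. The exposure-adjusted incidence rate (EAIR) gives 1.00 only if the hazard is constant. If the hazard halves after Week 24 in both arms, then at p = 5% cumulative hazard to Week 52 is 0.05129 × (1 + 0.5 × 28/24) = 0.0812 and incidence is 7.8%. The crude ratio is 1.56, while the EAIR ratio is about 0.74, so remibrutinib would look about 26% safer than it is.

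**The case against.** The strongest reply is that the right comparison is already planned. The primary-analysis double-blind rows of Tables 2-13 and 2-14 give LOU064 against placebo over 24 weeks for every output named. That analysis is triggered only once all participants have passed Week 24 or left early, so those tables should be essentially complete. This stands. A reader might infer that no matched comparison exists, or that it cannot be recovered; the documents do not support either.

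SAP 2.13 says only that the primary analysis may be conducted. But it also places all formal testing there, and the opening of Protocol 12 treats that analysis as planned, so it is unlikely to be skipped. A smaller gap remains. AE coding uses the MedDRA version current at each analysis (SAP 5.2) and AESI the latest retrieval strategy (2.7.1.1), so primary-analysis tables need not agree with final ones.

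Other mitigations also count. The 2.7.1 wording on study period could be read as covering the double-blind period at the final analysis, but the final rows of Tables 2-2, 2-13 and 2-14 do not carry it through. Exposure in subject-years is reported by group (2.4.1), which exposes the imbalance and allows rough rates. Fatal SAEs fall within the SAE EAIR. Infections, bleeding and cytopenias have double-blind counts and occurrence rates by time interval (2.7.1.1). No safety hypothesis is tested.

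A second tempting inference is that equal risk would look doubled throughout. That holds only for uncommon to moderately common events under a roughly constant hazard with little drop-out. It does not hold for visit-driven laboratory notables or front-loaded events.

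**Conclusion.** The point holds as one of presentation. In the entire-study rows, the outputs in the last column of Table 2-13 and the laboratory notables are crude percentages over unequal windows, and the final analysis lists nothing matched beside them. With identical risk, the crude ratio would be about 1.8 to 2.1 for placebo incidences of 3% to 30% under a constant hazard and full 52-week exposure, and slightly more with the 28-day tail. At incidences up to 10% it would be about 1.45 to 1.7 for front-loaded events and about 1.4 to 1.6 for visit-driven laboratory notables. Drop-out lowers the ratio. At the primary analysis the effect is smaller where the cut-off truncates remibrutinib exposure. All incidences and hazard shapes are assumptions. No efficacy result or error rate is touched, and the matched tables at the primary analysis limit the harm.

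**What to change.** 1. In Table 2-13, add EAIR to the last column for the entire-study rows of both analyses.
2. In the final-analysis rows of Tables 2-13 and 2-14, add a double-blind row (LOU064 against placebo, 0 to 24 weeks), or state that the primary-analysis double-blind tables are carried into the final report, with their coding version. Align Table 2-2 and the 2.7.1 text.
3. State that between-arm safety comparisons are read from the double-blind tables, and that entire-study EAIR is long-term description, because a changing hazard can distort it.

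The cost is a few more tables from existing programs and a sentence or two in the SAP. No new data are needed.

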2.7.1.1 Adverse events of special interest / grouping of AEs

Adverse events of special interest (AESI) for remibrutinib (such as risks defined in the Safety Profiling Plan, Risk Management Plan or topics of interest regarding signal detection or routine analysis) will be defined based on the latest Case Retrieval Strategy (eCRS). The comprehensive search of AESI will be performed for all TEAEs.

The number (and percentage) of participants with AESI will be summarized by safety topic of interest (i.e. risk name) and PT for study period and treatment group. Exposure adjusted incidence rate will also be provided by treatment group for the double-blind period and the entire study period.

In addition, for the selected AESIs (Infections, Bleeding, Cytopenias), the number of AESI events will be summarized by safety topic of interest (i.e., risk name) for study period and treatment group.

Summaries will also include the exposure adjusted occurrence rate and the corresponding 95% CI, the number of events per participant, time to onset of first event, duration of the events, the severity of the events, the outcome of events, treatment related events, the action taken with the study treatment for each event and duration of study drug interruption for events leading to study drug interruption.

- Exposure Adjusted Occurrence Rate (EAOR) will be calculated as follows:

EAOR = $100 * \text{total number of events} / \text{total exposure subject-time (years)}$

The exact Poisson 95% CIs (Garwood 1936, Sahai and Khurshid 1993) will be used. Please see [Section 5.4.2.5](#) for details.

For duration of study drug interruption (in days), once the events leading to study drug interruption are selected, the drug interruption occurred within 7 days of the event onset date will be considered. If there are more than one interruption, only the first interruption will be considered.

For the selected AESIs (Infections, Bleeding, Cytopenias), during the double-blind period, the number of events (per risk name), EAOR, and number of participants at risk occurring between 0-≤4 weeks, 4-≤12 weeks, 12-<24 weeks will be displayed by treatment group.

